4.1 Recruitment

Patients will be recruited at the time of admission to the Labor and Delivery units at the Montefiore Hospitals – Einstein Campus at Weiler and Montefiore North, at which there are approximately 60 and 30, respectively, fetal demises diagnosed annually. Firstly the diagnosis of fetal death will be ascertained as per the standards of the unit by the attending physician. The medical team will counsel the patient on the induction of labor plan. Based on inclusion and exclusion criteria potential participants will be informed about the research, offered the opportunity to voluntarily contribute, and trained research staff will complete the informed consent process. The timing of consent will be sensitive to the needs of the participant. The research and therefore voluntary aspect of care will be clearly delineated. After documentation of consent and discussion of the research as indicated the participants will be randomized to the intervention or control arm. Both groups will receive emotional and physical support with induction of labor as per practice guidelines and standard of care by Montefiore physicians, faculty and staff irrespective of participation or assignment.

Patients in the interventional arm will ingest 200mg tab of mifepristone orally. This will coincide with or be implemented prior to the initiation of the induction of labor plan as delineated by the attending physician. The timing will be sensitive to the needs of the participant and the labor and delivery room staff.

Similarly, patients in the control arm will ingest a placebo tab orally with similar physical properties without the active ingredient. This will coincide with or be implemented prior to the initiation of the

induction of labor plan as delineated by the attending physician. The timing will be sensitive to the needs of the participant and the labor and delivery room staff.

In an effort to optimize recruitment, participation and the diversity of the participants, no parental consent will be obtained. This is consistent with other research that involves youth and addresses reproductive health needs, with the goal of protecting privacy and eliminating a potential sampling bias (Martinez-Garcia 2014, Reed 2008). The National Commission for the Protection of Human Subjects of Biomedical and Behavioral Research and the Society of Adolescent Medicine have advised that parental consent can be waived for minimal risk research that involves care that is legally rendered in the state (reproductive health services) and it is difficult to obtain parental consent (National Commission 1997, Santelli 2003). Pregnant teens are emancipated in New York State and are often faced with socially complex and unstable home environments (Alperen 2013, Malee 2013). They may not have a guardian who accompanies them to their clinic visits or accompany is present with them in the hospital during the admission for management of fetal demise.

4.2 Inclusion Criteria

1. Women ages 16-50
2. Women whose primary language is English
3. Intrauterine fetal death as confirmed by absence of cardiac motion on ultrasound by Attending physician at the time of admission to the hospital.
4. Estimated gestational age greater than 20 weeks
5. Hemodynamically stable
6. Women with one prior low transverse cesarean delivery

4.3 Exclusion Criteria

1. History of 2 or more low transverse cesarean deliveries
2. Prior classical cesarean delivery
3. History of abdominal myomectomy
4. Known or suspected allergic reaction to mifepristone
5. Known or suspected adrenal gland disease
6. Known or suspected bleeding diatheses or coagulopathies
7. Known or suspected use of QTc-prolonging medication
8. Known maternal medical or physical conditions that prohibits vaginal delivery
9. Patients in active labor, with cervical dilation greater than 6 cm.

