In July of 2015, the CDC released the most updated statistical report on fetal and perinatal mortality. There were 23,595 documented fetal deaths in the year 2013, gestational age 20 weeks and greater. Minority and marginalized women are disproportionately affected; with black women comprising 26% and Hispanic women comprising 20% of the reported cases [34]. Our Bronx population includes these vulnerable populations, who stand to gain the most from evidence based protocols and improvements in the management of fetal demise. The community surrounding our Montefiore Weiler and Wakefield labor and delivery is identified as 45.3% Black and 58.4% Hispanic by US Census data [35]. Safely shortening the length of labor induction can greatly benefit the emotional and medical safety of our patients. A prolonged induction puts a woman at increased risk for: coagulopathy, sepsis, hemorrhage, and complications that require surgical intervention [22]. Mifepristone has a well-tested and known safety profile and has been proven to optimize the effects of misoprostol, which is the standard medication for induction of labor in the setting of fetal demise [6].

1.2 Hypothesis:

The addition of mifepristone, when compared to placebo, to the standard accepted methods of induction of labor will expedite time to delivery of the fetus in women with intra-uterine fetal demise at 20 weeks gestational age and greater.

1.3 Objectives:

1. To compare time to delivery of fetus after administration of mifepristone or placebo at the onset of labor induction.
2. To calculate the duration of induction and hospitalization time among the two groups including time to delivery of placenta, duration of time on labor and delivery, time as an inpatient, and number of nights in the hospital.
3. To determine the number of women, in each arm of the study, who require surgical interventions due to a failed induction or retained products of conception.

4. To determine if administration of mifepristone augments misoprostol, oxytocin and mechanical cervical dilation.
5. To explore the overall incidence of complications and their association with mifepristone use, such as febrile morbidity, infection requiring antibiotics, or transfusion.

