6. To assess whether simultaneous start of induction of labor with misoprostol after mifepristone administration versus subsequent administration or delays in the administration of misoprostol after mifepristone administration makes a difference in the time to delivery of the fetus and to assess the optimal lag time between the two medications.

1.4 Expected Outcomes:

It is expected that the addition of mifepristone will allow for more an expeditious delivery of the fetus among women who present with fetal demise greater than 20 weeks gestation age. It is the intention of the researchers that our results will be submitted for internal quality improvement assessment, scientific meeting presentation and peer review publication. We hope to impact our institutional practice as well as regional and national guidelines regarding the management of second and third trimester fetal demise.

II Study Design

2.1 Proposed Protocol:

We propose a double blinded, randomized, placebo-controlled clinical trial at the time of initiation of induction of labor for fetal demise at 20 weeks gestational age or greater.

1. Diagnose fetal demise: confirm absence of fetal heart motion by attending physician as per the institutional standards and protocols.
2. Confirm gestational age at presentation to labor and delivery based on available medical records and/or ultrasonography as per standard practice and institutional protocols.
3. Based on inclusion and exclusion criteria potential participants will be informed about the research, offered the opportunity to contribute, and trained research staff will complete the informed consent process. After documentation of consent and discussion of the research as indicated the participants will be randomized to the intervention or control arm. Both groups will receive emotional and physical support with induction of labor as per practice guidelines and standard of care by Montefiore physicians, faculty and staff irrespective of participation or assignment.

4. Interventional Arm: Ingest 200mg tab of mifepristone orally. This will coincide with or be implemented prior to the initiation of the induction of labor plan as delineated by the attending physician. The timing will be sensitive to the needs of the participant and the labor and delivery room staff.

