3.1 Study Drug Information

Mifepristone is a 19-nor-steroid derivative of norethindrone that competitively binds to progesterone and glucocorticoid receptors, with antagonist effect. The majority of the drug is absorbed through the gut (70%), it then undergoes demethylation and hydroxylation in P-450 microenzyme systems, namely CYP3A4 [18]. Subsequent monodemethylated, didemethylated and hydroxylated metabolites all maintain significant receptor activity[19]. Mifepristone and its metabolites are bound to alpha 1 acid glycoprotein in serum (AAG); saturation is reached with 100 mg of mifepristone. Peak plasma concentrations are reached within 1-2 hours of ingestion, with rapid distribution, alpha half-life of 1.4 hours, and a long beta half-life, elimination time of 20-30 hours [18]. Dosage regimens of 200 mg or more quickly saturate AAG and with the elaboration of metabolites nonlinear pharmacokinetics results in a large pool of biologically active substrates [19]. The physiologic effects of mifepristone include decidual detachment, necrosis, capillary regression, cervical softening and potentiation of myometrial contractions through the loss of progesterone's inhibitory effects [20]. This profile lends compelling support that mifepristone can confer tissue changes and procedural benefit within hours of administration. Of note, since Mifepristone is mainly metabolized by microenzyme CP3A4, the study will thoroughly review patients' medications/substances that may have the potential to induce/inhibit this enzyme. The safety and toxicity profiles of mifepristone are excellent. The FDA approved regimens for medication abortion in the US includes a dose of 800 mg and does not require any consideration or contraindication for women who are taking cytochrome inducing or inhibiting agents. It is not anticipated that many young, pregnant patients will be on such drugs; however, if a significant difference of patients' intake of such medications is noticed among the study arm compared to the control arm, the analysis of the outcomes will take that into account as a possible confounder, ie. exclude such patients in sub-analysis or control for this as a confounder.

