4.4 Participant Timeline

1. The patient receives a diagnosis of intrauterine fetal demise at 20 weeks gestational age or greater.
2. Patient must meet inclusion and exclusion criteria of study.
3. Patient verbally consents to the delivery plan and is a candidate for induction at a Montefiore labor and delivery (Wakefield or Weiler-Einstien Hospitals).
4. Participants will be informed about the research, offered the opportunity to contribute, and trained research staff will complete the informed consent process.
5. After documentation of consent and discussion of the research as indicated the participants will be randomized to the intervention or control arm. Both groups will receive emotional and physical support with induction of labor as per practice guidelines and standard of care by Montefiore physicians, faculty and staff irrespective of participation or assignment.
6. With prior assignment based on the randomization scheme medications will be maintained in secure medical dispensing equipment consistent with Montefiore standards (labor and delivery Pyxis will be used). Medications will be individually placed in sequentially numbered, sealed opaque containers. Research team will source and dispense medication to participants.
6. Patient's labor course is routinely monitored and documented in EMR by all participating providers.

V Randomization

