The hospital staff will maintain medical records as per standard of care. The research team will assign a unique numerical participant identifier with enrollment and allocation of participants. As previously mentioned this identifier will correspond with the information on the sealed medication envelope. Case report forms (CRF) will capture relevant data such as: medication administration time points, clinical events and secondary outcomes. Nursing, pharmacy and medical records will be reviewed to assure accuracy and completeness. Data proofing and collection will be completed by persons blinded to treatment assignment. Intake measures will include: age, socio-economic status, gestational age, method of attainment of gestational age, insurance, gravidity and parity, previous cesarean deliveries, medical history, most recent hemoglobin and hematocrit. Admission data will include cervical exam, membrane intact or rupture status, and vital signs. Secondary outcomes, additional interventions, and adverse events will be captured on the CRF. Due to the fact that participants will be inpatient for the duration of their induction and post-partum course, we do not anticipate any significant withdrawals, deviations or incomplete data sets. Patient identifiers will be secured in locked and protected environments. The CRF and abstracted data will not have any patient identifiers.

VII Statistical Guidelines

7.1 Sample Size:

Based on a review of the literature, institutional charts and clinician experience, the mean time to delivery of fetus is projected to be 24 hours with a standard deviation of 6 hours. To detect a change in 4 hours, with a two-sided alpha of 0.05 and power of 0.8: 37 persons would be needed in each group for a total of 74 persons enrolled in the study. The effect of 4-hour reduction is chosen because it is considered a clinically significant reduction.

7.2 Analysis:

An intention to treat analysis will be completed. Two sample t-test and Wilcoxon rank sum test will be calculated for the primary outcome of time to delivery of fetus. Other secondary outcomes will be described with descriptive statistics and compared with ANOVA or Chi square analysis.

VIII Ethical Consideration

8.1 Confidentiality:

The participants, providers, and research team will all be blinded for the duration of the study. The patients' medical information is protected under HIPAA, therefore only staff directly involved in the

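### Eligibility does not clearly keep out women already in labor at 6 cm or less, although the trial asks about drug given at the onset of induction; the likely cost is power, of unknown size

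*Combined protocol and SAP*

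**What the plan says.** **The question.** Objective 1 in section 1.3 is "To compare time to delivery of fetus after administration of mifepristone or placebo at the onset of labor induction". Section 2.1 sets the randomised comparison "at the time of initiation of induction of labor for fetal demise at 20 weeks gestational age or greater". On the timing of the tablet, 2.1 items 4 and 5 say "This will coincide with or be implemented prior to the initiation of the induction of labor plan as delineated by the attending physician".

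**Who may enter.** Exclusion 9 in 4.3 is "Patients in active labor, with cervical dilation greater than 6 cm". Nothing else in 4.2 or 4.3 mentions labor, contractions or ruptured membranes. Section 4.4 item 3 adds that the patient "is a candidate for induction at a Montefiore labor and delivery", without saying what makes her one.

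**How such women are handled later.** Section V describes variable-block allocation and names no stratification factor. Section VI records the admission cervical exam and membrane status. Section 7.2 plans an intention-to-treat analysis with a two-sample t-test and a Wilcoxon rank sum test, and gives neither a covariate.

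**Sample size.** Section 7.1 states that "the mean time to delivery of fetus is projected to be 24 hours with a standard deviation of 6 hours". The target is "To detect a change in 4 hours, with a two-sided alpha of 0.05 and power of 0.8", giving 37 per group.

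**Drug onset.** Section 3.1 says "Peak plasma concentrations are reached within 1-2 hours of ingestion" and argues that tissue changes and benefit can follow within hours.

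**The concern.** Eligibility is wider than the question. A woman contracting at 6 cm or less on admission meets every listed criterion unless the undefined candidacy step stops her. If she is randomised, part or all of her labor is not the product of the induction that the trial studies.

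Two things could follow. If the drug does little for her, she pulls the mean difference toward zero. If she also delivers well before 24 h, she adds a cluster of short times and widens the SD. The sample size allows for neither, and planned power is only just above 80%. A true 4-hour benefit among women who are actually induced could then be missed.

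**Working it through.** **Step 1. Reproduce the plan's figure.** Inputs from 7.1: difference 4 h, SD 6 h, two-sided alpha 0.05, power 0.8. The t-test calculation gives 36.3, rounded up to 37 per arm, which matches. Power at 37 per arm is 0.808.

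**Step 2. Model for women already in labor.** Let a share f of each arm be already in labor, with delivery times of mean m and SD s in both arms (no drug effect). All others follow 24 h against 20 h with SD 6 h. The values of f, m and s are assumptions; the documents give none of them.

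- Mean difference = 4(1 − f).
- Variance in an arm with mean μ for the other women = (1 − f)·36 + f·s² + f(1 − f)(μ − m)².
- The SD is the square root of the average of the two arm variances.

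**Step 3. Worked case: f = 0.10, m = 6, s = 3.**

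- Difference = 4 × 0.90 = 3.6 h.
- Control variance = 32.4 + 0.9 + 0.09 × 18² = 62.46.
- Mifepristone variance = 32.4 + 0.9 + 0.09 × 14² = 50.94.
- SD = √56.70 = 7.53 h. Power at 37 per arm = 0.528.

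**Step 4. Range.**

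| Assumption for women in labor | Share | Difference (h) | SD (h) | t-test power | Per arm for 80% |
|---|---|---|---|---|---|
| None enrolled | 0 | 4.0 | 6.00 | 0.81 | 37 |
| Mean 6 h, SD 3 h, no effect | 5% | 3.8 | 6.86 | 0.65 | 53 |
| Same | 10% | 3.6 | 7.53 | 0.53 | 70 |
| Mean 12 h, SD 6 h, no effect | 5% | 3.8 | 6.40 | 0.71 | 46 |
| Same | 10% | 3.6 | 6.74 | 0.62 | 56 |
| No effect, overall SD stays 6 h | 5% | 3.8 | 6.00 | 0.77 | 41 |
| Same | 10% | 3.6 | 6.00 | 0.72 | 45 |

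Five percent of 37 is about two women per arm. At a 1% share, power is 0.78 (mean 6 h) or 0.79 (mean 12 h), so the loss is then minor.

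**Step 5. Does the loss need the drug to fail in these women?** Give them the full 4 h benefit, with means of 12 h on control and 8 h on mifepristone and SD 6 h. The difference stays at 4 h. At a 10% share the variance in each arm is 36 + 0.09 × 12² = 48.96, so SD = 7.00 h and power is 0.68. At 5% it is 0.74. Part of the loss comes from spread alone.

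**Step 6. Wilcoxon test.** In a simulation of 10,000 trials with mean 6 h, SD 3 h and no effect, Wilcoxon power is 0.78 with no such women, 0.70 at 5% and 0.59 at 10%. The t-test gives 0.81, 0.65 and 0.53. The rank test softens the loss but does not remove it.

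**The case against.** **The candidacy step may screen many of these women out.** Section 4.1 has the team counsel the patient on the induction plan before research is offered, and dosing is tied to that plan. A woman in spontaneous labor with no induction planned fits this sequence poorly. This stands in part. But the term is undefined, and if candidacy already barred all laboring women, exclusion 9 would have nothing to do.

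**Exclusion 9 can be read as defining active labor by 6 cm.** That is a fair reading. On it, a woman contracting below that point still enters, so the gap remains and the wording needs clarifying either way.

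**A reader might infer that these women deliver too soon for the drug to act.** The documents do not support that. They give no delivery times for such women, and a peak at 1–2 h with benefit within hours leaves room for some to respond.

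**The projection may already include them.** Section 7.1 draws partly on institutional charts. If those charts contain women who arrived in labor, some of the added variance is counted twice and the loss is smaller. This stands.

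**Broad entry can be defended.** Sections 1.1 and 3.1 frame the trial around practical management, and randomisation balances these women between arms in expectation. This answers any charge of bias, but not the mismatch with the stated question.

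**Conclusion.** The concern holds as a gap between eligibility and question, with a possible loss of power. Women already in labor at 6 cm or less are not clearly kept out, and neither randomisation nor analysis takes account of them.

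At an assumed share of 5% to 10% with no drug effect, power falls from 0.81 to between 0.65 and 0.53 (mean 6 h, SD 3 h) or between 0.71 and 0.62 (mean 12 h, SD 6 h). None of these figures is a forecast: share, delivery times and absence of effect are all assumed, and at a share near 1% little is lost.

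A reader might also infer a biased treatment comparison. That does not follow: the intention-to-treat comparison remains valid for the women enrolled. What suffers is the chance of detecting the effect and the clarity of whom the result describes. It merits correction mainly because the correction is cheap and the power margin is thin.

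**What to change.** 1. Reconcile exclusion 9 with the hypothesis in 1.2, objective 1 and the candidacy requirement in 4.4, so that women already in labor with no induction planned are not randomised. State in 4.4 what being a candidate for induction means. The clinical threshold is for the investigators to set.
2. In 7.2, prespecify adjustment of the primary comparison for the admission cervical exam, which the CRF already collects. This covers women who come in with some cervical change but are still to be induced. It can recover part of the power lost to extra variance, but not the part lost to a smaller mean difference.

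**Cost.** A short amendment to the eligibility text and one sentence in the analysis section. Eligible women would be slightly fewer, from about 90 demises a year at the two sites (60 + 30, section 4.1), by an amount the documents do not allow one to estimate. The result would not cover women who arrive in labor. Contractions and the induction plan are not among the admission items listed in section VI, so sites may need to record whatever the revised criterion relies on.

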4.4 Participant Timeline

1. The patient receives a diagnosis of intrauterine fetal demise at 20 weeks gestational age or greater.
2. Patient must meet inclusion and exclusion criteria of study.
3. Patient verbally consents to the delivery plan and is a candidate for induction at a Montefiore labor and delivery (Wakefield or Weiler-Einstien Hospitals).
4. Participants will be informed about the research, offered the opportunity to contribute, and trained research staff will complete the informed consent process.
5. After documentation of consent and discussion of the research as indicated the participants will be randomized to the intervention or control arm. Both groups will receive emotional and physical support with induction of labor as per practice guidelines and standard of care by Montefiore physicians, faculty and staff irrespective of participation or assignment.
6. With prior assignment based on the randomization scheme medications will be maintained in secure medical dispensing equipment consistent with Montefiore standards (labor and delivery Pyxis will be used). Medications will be individually placed in sequentially numbered, sealed opaque containers. Research team will source and dispense medication to participants.
6. Patient's labor course is routinely monitored and documented in EMR by all participating providers.

V Randomization

Allocation methods will be variable block randomization (blocks of 2&6, by computer generated random number sequence. Best practices will be implemented to assure the maintenance of randomization and blinding. The randomization scheme will be kept at a separate secure research site and researchers will not have access to this scheme until the analysis phase, following completion of the data collection process and enrollment. The Montefiore research pharmacy will be involved in the storage, packaging, monitoring and utilization of both placebo and study medications. The placebo and study medications will be maintained in secure medical dispensing equipment consistent with Montefiore standards (labor and delivery Pyxis). Medications will be individually placed in sequentially numbered, sealed opaque containers with a unique participant identifier that will correspond with the patient identifier the participant receives upon enrollment. Participants, research staff, and the data collection and analysis teams will be blinded to contents of each pill. The mifepristone and placebo tablets will be obtained from Danco pharmacies where the placebo has been specifically developed to have similar physical properties to the mifepristone tablet.

VI Data Collection

The hospital staff will maintain medical records as per standard of care. The research team will assign a unique numerical participant identifier with enrollment and allocation of participants. As previously mentioned this identifier will correspond with the information on the sealed medication envelope. Case report forms (CRF) will capture relevant data such as: medication administration time points, clinical events and secondary outcomes. Nursing, pharmacy and medical records will be reviewed to assure accuracy and completeness. Data proofing and collection will be completed by persons blinded to treatment assignment. Intake measures will include: age, socio-economic status, gestational age, method of attainment of gestational age, insurance, gravidity and parity, previous cesarean deliveries, medical history, most recent hemoglobin and hematocrit. Admission data will include cervical exam, membrane intact or rupture status, and vital signs. Secondary outcomes, additional interventions, and adverse events will be captured on the CRF. Due to the fact that participants will be inpatient for the duration of their induction and post-partum course, we do not anticipate any significant withdrawals, deviations or incomplete data sets. Patient identifiers will be secured in locked and protected environments. The CRF and abstracted data will not have any patient identifiers.

VII Statistical Guidelines

7.1 Sample Size:

Based on a review of the literature, institutional charts and clinician experience, the mean time to delivery of fetus is projected to be 24 hours with a standard deviation of 6 hours. To detect a change in 4 hours, with a two-sided alpha of 0.05 and power of 0.8: 37 persons would be needed in each group for a total of 74 persons enrolled in the study. The effect of 4-hour reduction is chosen because it is considered a clinically significant reduction.

7.2 Analysis:

An intention to treat analysis will be completed. Two sample t-test and Wilcoxon rank sum test will be calculated for the primary outcome of time to delivery of fetus. Other secondary outcomes will be described with descriptive statistics and compared with ANOVA or Chi square analysis.

VIII Ethical Consideration

8.1 Confidentiality:

The participants, providers, and research team will all be blinded for the duration of the study. The patients' medical information is protected under HIPAA, therefore only staff directly involved in the

patients' care and the primary research team will access the participants' medical records. All personal identify information will be removed from CRF. A unique participant identifier will be utilized for all data collection and analysis. In a separate locked and secured location the consent forms will be secured with a log of participants enrolled in the research.

8.2 Dissemination Policy:

Data collected during the study by labor and delivery team is confidential and protected by HIPPA. Abstracted data without patient identifier will be entered into CRF. The data will then be analyzed and reported.

8.3 Declaration of Interest:

The investigatorshave nothing to declare. Our purpose is to enrich the current body of knowledge on induction of labor for an intrauterine fetal demise in the second and third trimester.

8.4 Potential Benefits:

If Mifepristone expedites the delivery of the demised fetus, women in the control of the arm of the study will benefit tremendously from participating in the study as their induction will be shorter. This outcome has important consequences as it will avoid secondary complications from long inductions such as maternal infections and surgery. Additionally, a quicker induction time may ameliorate the emotional suffering of the patients.

8.5 Adverse Event and Safety Monitoring Board:

A safety monitoring board will be identified consisting of two clinician scientists who are familiar with scope of clinical practice but are not directly involved in the research. These physicians will review adverse events and work closely with the principle investigator and research team to assure that safety and reporting standards are maintained at a high level. The principle investigator will also actively review all outcomes for the patients throughout the course of the study, and will remained blinded to their treatment. Data will be abstracted within 72 hours of enrollment from the electronic medical record onto case report forms for the majority of participants. Timing regarding abstraction of serious adverse events onto case report forms is delineated below. The PI will review all CRFs and cross check to the medical record for accuracy every 6 weeks. There will be quarterly communications between the PI and monitoring board regarding adverse events and a written annual reports of these communications will be compiled regarding the review and assessments by the monitoring board. The PI and research team will

convene weekly for the first few months and then monthly thereafter to assure that the application of the protocol, recruitment and data collection practices are all in compliance. All adverse event and case report forms will be available to the monitoring board, and reports of this information will

An adverse event is any symptoms, sign, illness or experience that develops or worsens in severity during the course of the study. A number of adverse events are expected in the course of the management of fetal demise and induction of labor including, pain and bleeding. Information as noted in the medical records will be abstracted in the CRF and compiled as secondary outcomes. Events that are determined to be both unexpected and related to the study medication will be entered into the CRF as well as a separate adverse event form. All serious adverse events will be reviewed by the PI, data safety monitoring board and submitted to the IRB within 48 hours. Other adverse events will be reviewed by the PI, data safety monitoring board, and submitted within one week. Events that meet International Conference on Harmonization (ICH) criteria for a serious adverse event include volunteers who experience any of the following during the course of their enrollment: death, life-threatening event, inpatient hospitalization or prolongation of existing hospitalization, occurrence that results in persistent or significant disability in capacity, congenital anomaly/birth defect, or other important medical event (may not be immediately life-threatening or result in death or hospitalization but may jeopardize the patient or may require intervention to prevent one of the events listed above). An important medical event is one that may not be immediately life threatening, but is clearly of major medical significance. It may jeopardize the subject, and may require intervention to prevent one of the other serious outcomes noted above. All serious adverse events will be reviewed by the PI, regardless of causality assessment. Serious adverse events will be reported to Montefiore Medical Center, the FDA, and Danco Laboratories, Inc. All information related to data and adverse events will be monitored by the principle investigator, [name].

XI Consent

